8.4.2 Clinical Laboratory

For the treatment-emergent laboratory assessments, the observed values and change from baseline values of the continuous hematology, coagulation, and chemistry results will be summarized in SI units at each visit by treatment group.

The number and percentage of subjects meeting at least 1 threshold analysis criterion event during the TE Period for the Treatment Period will be summarized by treatment group. The threshold analysis criterion shift from baseline will also be summarized for select laboratory parameters. The threshold analysis criteria are provided in [Appendix](#) .

For select liver function laboratory tests (alanine transaminase [ALT], aspartate transaminase [AST], alkaline phosphatase [ALP], and total bilirubin), a scatterplot of the maximum TE value versus the baseline value corresponding to xULN (upper limit of normal) will be presented. Further, a scatterplot of the maximum TE value of ALT and AST, separately, versus the maximum TE value of total bilirubin corresponding to xULN will also be presented by treatment group. For ALT, AST, and total bilirubin, box-and-whisker plots will be used to display raw values at each visit by treatment group.

Results of positive serum/urine pregnancy tests will be listed in individual subject data listings only. For the positive serum pregnancy listing, subjects with serum HCG which are abnormally high will be selected.

In addition, listings containing individual subject hematology, chemistry, coagulation, and urinalysis values will be provided. The listings will include data from both scheduled and unscheduled visits. A listing of subjects who meet the criteria of [(ALT>3xULN or AST>3xULN) and TBILI>2xULN] at any visit will be provided. This listing will include data from all visits (including unscheduled visits) and present values for ALT, AST, ALP, and total bilirubin.

8.4.3 Electrocardiogram

A summary of observed values and change from baseline values will be provided at each visit by treatment group for the following treatment-emergent ECG measurements (in msec): RR interval, PR interval, QT interval, QTcF interval, QRS duration, and heart rate (beats/minute).

The number and percentage of subjects meeting at least 1 threshold analysis criterion during the TE Period for the Treatment Period will be summarized by treatment group. The threshold analysis criteria are provided in [Appendix](#).

In addition, a listing containing individual subject ECG values will be provided. This listing will include data from both scheduled and unscheduled visits.

8.4.4 Vital Signs

For the treatment-emergent vital signs measurements, the observed values and change from baseline values will be summarized at each visit by treatment group. The following vital signs parameters will be summarized: systolic and diastolic blood pressure (mmHg), body temperature (°C), pulse rate (beats/minute), and respiratory rate (breaths/minute).

The number and percentage of subjects meeting at least 1 threshold analysis criterion during the TE Period for the Treatment Period will be summarized by treatment group. The threshold analysis criteria are provided in [Appendix](#).

In addition, a listing containing individual subject vital signs values will be provided. This listing will include data from both scheduled and unscheduled visits.

8.4.5 Pulse Oximetry

For the treatment-emergent pulse oximetry measurements, a summary of observed values and change from baseline values will be provided at each visit by treatment group for the percent of oxygen saturation.

The number and percentage of subjects with shift changes from baseline (normal/missing and low according to the reference range) to the lowest percent of oxygen saturation during the TE

Period for the Treatment Period will be summarized by treatment group. The reference range for normal oxygen saturation is specified as >95%, and <=95% for low oxygen saturation.

8.4.6 Ophthalmologic Examinations

Ophthalmologic examination results will be presented in individual subject data listings only.

8.4.7 Physical Examination

Abnormal PE findings will be presented in individual subject data listings only.

8.4.8 Supportive Safety Analysis

8.4.8.1 Adverse Events of Special Interest

For this study, elevated transaminases, creatine kinase elevations, rash, cataracts, hypoglycemia, and neuropsychiatric events as determined by MedDRA PTs in [Appendix](#) are considered adverse events of special interest (AESI).

For AESI during the TE Period for the Treatment Period, the following categories will be summarized by treatment group:

- Subjects with events
- Subjects with events by maximum severity
- Subjects with events leading to treatment discontinuation
- Subjects with events leading to treatment interruption
- Subjects with related events
- Subjects with serious events
- Subjects with related serious events
- Subjects with events leading to death
- Duration of events
- Time-to-onset of first event

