#### 9.8.1 Liver Function Tests

The central laboratory will notify the medical monitor of ALT or AST  $>3 \times \text{ULN}$  and total bilirubin  $>2 \times \text{ULN}$  that are derived from centrally submitted samples.

Subjects with new treatment-emergent ALT or AST elevations of  $>3 \times \text{ULN}$ , with or without total bilirubin  $>2 \times \text{ULN}$ , must be followed closely, including confirmatory testing performed by the central laboratory within 48 to 72 hours of the initial finding and subsequent close monitoring of ALT, AST, and bilirubin levels, as clinically indicated.

If a subject cannot return to the site for confirmatory testing, a local laboratory may be used. Local laboratory results must be reported immediately to the medical monitor, and the subject must have the tests repeated and sent to the central laboratory as soon as possible (ideally within 48 to 72 hours).

Study drug administration **must be interrupted** immediately (prior to confirmatory testing) if any of the following criteria are met:

- ALT or AST  $>8 \times \text{ULN}$
- ALT or AST  $>5 \times \text{ULN}$  for more than 2 weeks
- ALT or AST  $>3 \times \text{ULN}$ , in association with total bilirubin  $>2 \times \text{ULN}$  and/or clinical jaundice

A thorough investigation of potential causes should be conducted, and the subject should be followed closely for clinical progression.

Study drug administration **must be discontinued** if the following criterion is met:

- Subsequent ALT or AST values confirm the initial elevation that satisfied the interruption rule (above), and no convincing alternative etiology (e.g., acetaminophen use, viral hepatitis, alcohol ingestion) is identified, regardless of whether transaminase levels have improved

All subjects in whom treatment is discontinued for elevated transaminases (and bilirubin, as applicable) should have these levels monitored closely until levels normalize or return to baseline.

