## **12.3.4 Safety Analysis**

All safety analyses will be based on the data from the TE period for the Treatment Period for all subjects in the corresponding Safety Set for the Treatment Period, unless otherwise specified.

The overall safety profile of study drug will be assessed in terms of the following safety and tolerability assessments:

- Treatment-emergent adverse events (TEAEs)
- Clinical laboratory values (i.e., hematology, serum chemistry, coagulation, and urinalysis as applicable)
- Standard 12-lead ECGs
- Vital signs
- Pulse oximetry
- Ophthalmological examinations

Only descriptive analysis of safety will be performed and no statistical testing will be performed. The safety data during the Run-in Period will only be presented in listings, unless otherwise specified. Additional details will be provided in the SAP.

LFT elevations, creatine kinase elevations, rash, cataracts, hypoglycemia, and neuropsychiatric events will be designated as AEs of special interest.

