Appendix F: Criteria for Threshold Analysis

Table 11-3 Threshold Analysis Criteria for Laboratory Tests (as applicable)

Parameter	Threshold Analysis	Comments
Clinical Chemistry (LFT)		
ALT	>ULN - ≤3xULN >3x - ≤ 5xULN >5x - ≤ 8xULN >8x - ≤ 20xULN >20xULN	FDA DILI Guidance Jul 2009.
AST	>ULN - ≤3xULN >3x - ≤ 5xULN >5x - ≤ 8xULN >8x - ≤ 20xULN >20xULN	FDA DILI Guidance Jul 2009.
ALT or AST	(ALT>ULN - ≤ 3xULN) or (AST>ULN - ≤ 3xULN) (ALT>3x - ≤ 5xULN) or (AST>3x - ≤ 5xULN) (ALT>5x- ≤ 8xULN) or (AST>5x - ≤ 8xULN) (ALT>8x - ≤ 20xULN) or (AST>8x - ≤ 20xULN) ALT>20xULN or AST> 20xULN	FDA DILI Guidance
Alkaline Phosphatase	>ULN - ≤ 1.5xULN >1.5x - ≤ 2.5xULN >2.5x - ≤ 5x ULN >5x - ≤ 20x ULN >20x ULN	FDA DILI Guidance Jul 2009.
Total Bilirubin	>ULN - ≤ 1.5xULN >1.5x - ≤ 2xULN >2x - ≤ 3xULN >3x - ≤ 10xULN >10xULN	FDA DILI Guidance Jul 2009.
Direct Bilirubin	>ULN - ≤ 1.5xULN >1.5x - ≤ 2xULN >2x - ≤ 3xULN >3x - ≤ 10xULN >10xULN	FDA DILI Guidance Jul 2009.
Indirect Bilirubin	>ULN - ≤ 1.5xULN >1.5x - ≤ 2xULN >2x - ≤ 3xULN >3x - ≤ 10xULN >10xULN	FDA DILI Guidance Jul 2009.
ALT and Total Bilirubin	ALT>3xULN and TBILI>2xULN	FDA DILI Guidance Jul 2009.
AST and Total Bilirubin	AST>3xULN and TBILI>2xULN	FDA DILI Guidance Jul 2009.
(ALT or AST) and Total Bilirubin	(ALT>3xULN or AST>3xULN) and TBILI>2xULN	FDA DILI Guidance Jul 2009.

Table 11-3 Threshold Analysis Criteria for Laboratory Tests (as applicable)

Parameter	Threshold Analysis	Comments
GGT	>ULN - ≤ 2.5xULN >2.5x - ≤ 5xULN >5x - ≤ 20xULN >20xULN	CTCAE grade 1-4
Clinical Chemistry (NON-LFT)		
Albumin	<LLN - ≥ 30 g/L <30 - ≥ 20 g/L <20 g/L	CTCAE grade 1-3
Amylase	>ULN - ≤ 1.5xULN >1.5x - ≤ 2xULN >2x - ≤ 5xULN >5xULN	Criteria based upon CTCAE
Creatinine	>ULN - ≤ 1.5xULN >1.5x - ≤ 3xULN >3x - ≤ 6xULN >6xULN	CTCAE grades 1-4
Lipase	>ULN - ≤ 1.5xULN >1.5x - ≤ 2xULN >2x - ≤ 5xULN >5xULN	Criteria based upon CTCAE
Total protein	<LLN >ULN	No CTCAE
Creatine Kinase	>ULN - ≤ 2.5xULN >2.5x - ≤ 5xULN >5x - ≤ 10xULN >10xULN	CTCAE grades 1-4
Hematology		
Hemoglobin	Hgb decreased (anemia) <LLN - ≥ 100 g/L <100 - ≥ 80 g/L < 80 g/L	CTCAE grade 1-3
	Hgb increased >ULN - ≤ 20 g/L above ULN >20 g/L above ULN - ≤ 40 g/L above ULN >40 g/L above ULN	CTCAE grade 1-3
Platelets	Platelet decreased <LLN - ≥ 75.0 x 10e9 /L <75.0 - ≥ 50.0 x 10e9 /L <50.0 - ≥ 25.0 x 10e9 /L <25.0 x 10e9 /L	CTCAE grade 1-4
	Platelet increased >ULN	No CTCAE available
Reticulocytes/Erythrocytes (%)	<LLN >ULN	No CTCAE

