Appendix G: Adverse Events of Special Interest

Table 11-7 MedDRA Preferred Terms for Event of Special Interest	
Adverse event of special interest	MedDRA preferred terms [1]
Transaminase Elevations	Alanine aminotransferase abnormal, Alanine aminotransferase increased, Aspartate aminotransferase abnormal, Aspartate aminotransferase increased, Transaminases abnormal, Transaminases increased, Liver function test abnormal, Liver function test increased, Hypertransaminasaemia, Hepatic enzyme abnormal, Hepatic enzyme increased
Rash	AGEP-DRESS overlap, Acute generalised exanthematous pustulosis, Anal rash, Cutaneous vasculitis, Dermatitis, Dermatitis allergic, Dermatitis atopic, Dermatitis bullous, Dermatitis exfoliative, Dermatitis exfoliative generalised, Drug eruption, Drug hypersensitivity, Drug reaction with eosinophilia and systemic symptoms, Epidermal necrosis, Epidermolysis, Erythema multiforme, Erythrodermic atopic dermatitis, Exfoliative rash, Fixed eruption, Generalised bullous fixed drug eruption, Immune-mediated dermatitis, Lichen planus pemphigoides, Mucocutaneous rash, Mucocutaneous toxicity, Nodular rash, Oculomucocutaneous syndrome, Penile dermatitis, Perioral dermatitis, Periorbital dermatitis, Rash, Rash erythematous, Rash follicular, Rash macular, Rash maculo-papular, Rash maculovesicular, Rash morbilliform, Rash papular, Rash papulosquamous, Rash pruritic, Rash pustular, Rash rubelliform, Rash scarlatiniform, Rash vesicular, SJS-TEN overlap, Scrotal dermatitis, Severe cutaneous adverse reaction, Skin exfoliation, Skin necrosis, Skin toxicity, Stevens-Johnson syndrome, Systemic contact dermatitis, Toxic epidermal necrolysis, Toxic skin eruption, Type IV hypersensitivity reaction, Urticaria, Urticaria papular, Urticaria vesiculosa, Urticarial dermatitis, Urticarial vasculitis, Vasculitic rash
Cataracts	Atopic cataract, Cataract, Cataract congenital, Cataract cortical, Cataract diabetic, Cataract nuclear, Cataract subcapsular, Lens discolouration, Lenticular opacities, MYH9-related disease, Radiation cataract, Toxic cataract
Hypoglycemia	Blood glucose decreased, Hypoglycaemia, Glycopenia, Hyperinsulinaemic hypoglycaemia, Hypoglycaemia unawareness, Hypoglycaemic coma, Hypoglycaemic encephalopathy, Hypoglycaemic seizure, Hypoglycaemic unconsciousness, Shock hypoglycaemic

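### The SAP turns the protocol's special-interest category of LFT elevations into transaminase elevations without declaring it, and lists no bilirubin-, ALP- or GGT-specific term

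*SAP*

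**What the plan says.** Protocol 12.3.4 sets the categories: "LFT elevations, creatine kinase elevations, rash, cataracts, hypoglycemia, and neuropsychiatric events will be designated as AEs of special interest". It gives no term list and leaves further detail to the SAP.

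SAP 8.4.8.1 names "elevated transaminases, creatine kinase elevations, rash, cataracts, hypoglycemia, and neuropsychiatric events as determined by MedDRA PTs". Five of the six categories carry over; the hepatic one changes. The matching row of Appendix G Table 11-7 is headed Transaminase Elevations. Its terms begin "Alanine aminotransferase abnormal, Alanine aminotransferase increased, Aspartate aminotransferase abnormal, Aspartate aminotransferase increased, Transaminases abnormal, Transaminases increased" and end "Liver function test abnormal, Liver function test increased, Hypertransaminasaemia, Hepatic enzyme abnormal, Hepatic enzyme increased".

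Elsewhere the SAP uses the liver-function label more widely. Section 8.4.2 introduces its liver plots with "For select liver function laboratory tests (alanine transaminase [ALT], aspartate transaminase [AST], alkaline phosphatase [ALP], and total bilirubin". In Appendix F Table 11-3, the block whose heading begins "Clinical Chemistry (LFT" also holds ALP, total, direct and indirect bilirubin, and GGT; the non-LFT block starts only after GGT.

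SAP 2.1, which is the place to record departures from the protocol, says not applicable.

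**The concern.** The protocol named a category and the SAP reports a smaller one under a different name, without saying so. A reader who takes the hepatic AESI row as the protocol's LFT elevations would be reading a count of something else.

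The term list also fits neither label. It is broader than transaminase elevations, because it includes generic liver-test and hepatic-enzyme terms. It is narrower than LFT elevations, because it has no term specific to bilirubin, ALP or GGT. A bilirubin rise coded as a generic liver-function-test abnormality is in, and the same rise coded to a bilirubin term is out. Inclusion then depends on how the site worded the event and how it was coded.

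At stake is the completeness of one grouped safety summary in a 52-week comparison of two regimens. No efficacy result is involved.

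**Working it through.** The plan gives no figure to reproduce, so the check is a comparison of texts and a count of terms.

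**Step 1: the two category lists.** Creatine kinase elevations, rash, cataracts, hypoglycemia and neuropsychiatric events appear in both documents. The sixth is LFT elevations in Protocol 12.3.4 and elevated transaminases in SAP 8.4.8.1.

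**Step 2: the hepatic row of Table 11-7.**
- Specific to transaminases: four ALT or AST terms, two terms naming transaminases, and hypertransaminasaemia. 4 + 2 + 1 = 7.
- Generic: two liver-function-test terms and two hepatic-enzyme terms. 2 + 2 = 4.
- Specific to bilirubin, ALP or GGT: 0.
- Total: 7 + 4 + 0 = 11.

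**Step 3: what the SAP itself calls a liver function test.** Section 8.4.2 names ALT, AST, ALP and total bilirubin. Table 11-3 adds direct and indirect bilirubin and GGT. No outside definition is needed to see that the SAP's usage is wider than its AESI row.

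**Step 4: what an excluded event loses.** SAP 8.4.8.1 lists 10 summaries for each AESI. Eight have a counterpart in the TEAE tables of SAP 8.4.1, which are by SOC and preferred term and by treatment group:
- any event
- maximum severity
- leading to discontinuation
- leading to interruption
- related
- serious
- related serious
- leading to death

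The other 10 − 8 = 2, duration and time to onset of the first event, have none.

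For the eight, the information survives only term by term. A grouped count of subjects cannot be rebuilt by adding preferred-term rows, because one subject may appear under several terms.

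**Step 5: direction.** Leaving terms out can only lower the number of subjects with a hepatic AESI or leave it unchanged. It falls by the subjects whose only LFT event is coded to an analyte-specific term. A subject who also has an event coded to a listed term is still counted, but the analyte-specific event contributes nothing to that subject's maximum severity, duration or time to onset.

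**The case against.** The strongest reply is that the protocol never defines LFT elevations and leaves detail to the SAP, so choosing the preferred terms there is the expected step. The LFT heading in Table 11-3 groups laboratory parameters and does not define an adverse-event category. This stands in part: the breadth of the list is a judgement the SAP may make. But 8.4.8.1 also replaces the category's name with a narrower one, and that is a change SAP 2.1 should record.

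The second reply is that little is lost. This also stands in large part. Four of the 11 terms are generic and still capture some bilirubin, ALP or GGT events. Excluded events appear in the general TEAE tables. Laboratory values are covered separately: SAP 8.4.2 plans summaries by visit, threshold counts, scatterplots, and a listing of subjects with ALT or AST above 3 × ULN together with total bilirubin above 2 × ULN. None of these outputs gives the grouped count, or the duration and time to onset, for the omitted adverse events.

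Two stronger readings are tempting.

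- A reader might infer that all bilirubin, ALP and GGT events disappear from the hepatic summary, or from the safety report. The documents do not support either: the generic terms keep some in the AESI row, and the TEAE tables keep the rest in the report.
- A reader might infer from Protocol 9.8.1, which provides for "subsequent close monitoring of ALT, AST, and bilirubin levels, as clinically indicated", that the study-drug interruption rule itself requires bilirubin events, or jaundice, in the AESI list. It does not. Every interruption criterion there needs an ALT or AST elevation, bilirubin or jaundice counts only alongside one, and ALP and GGT do not appear. Jaundice is also a clinical sign, so it lies outside a category of laboratory elevations.

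**Conclusion.** The point holds as an undeclared narrowing of a category the protocol named, with a term list that makes inclusion depend on coding. The loss is limited to the grouped hepatic AESI count and its duration and time-to-onset summaries, for events coded to bilirubin-, ALP- or GGT-specific terms.

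Its size in events is unknown. It depends on how many such events occur and how they are coded, and neither document gives a basis for an estimate. Safety is summarized descriptively with no testing (SAP 8.4), so no inference changes, and the primary and key secondary efficacy analyses are untouched.

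The conclusion assumes that LFT in Protocol 12.3.4 carries the meaning the SAP gives it in 8.4.2 and Table 11-3. If the sponsor meant transaminases only, the protocol and SAP still disagree in wording and the difference still needs to be recorded.

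**What to change.** Amend the SAP before database lock, as SAP Section 3 allows:

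- In 8.4.8.1 and Table 11-7, restore the category name LFT elevations, to match Protocol 12.3.4.
- Add the increased and abnormal preferred terms specific to bilirubin, ALP and GGT to that row.
- Report transaminase elevations, defined by the current 11 terms, as a subset row, so that the narrower summary is still available.

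If the sponsor prefers the narrower category, the minimum is to record and justify it in SAP 2.1 and to explain why the four generic terms stay in a row labelled as transaminases.

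The cost is a longer term list, one extra row in the AESI output and a hepatic count that may be slightly higher. No new data collection is needed, and the change can be made while treatment is still blinded.

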### **11.6.6 Ophthalmologic Examination**

Ophthalmologic examinations will be conducted only for subjects who are <18 years of age on the date of informed consent. The examination does not need to be completed if there is documentation of bilateral lens removal for the subject.

All examinations will be conducted by a licensed ophthalmologist or optometrist and will include:

- measurement of best-corrected distance visual acuity of each eye; and
- pharmacologically-dilated examination of the lens with a slit lamp.

The screening examination does not need to be conducted if there is documentation of an examination meeting the protocol requirements that was conducted within 3 months before the date of informed consent.

In addition to the screening ophthalmologic examination, subjects who are <18 years of age on the date of informed consent and who have completed at least 12 weeks of study drug treatment will have a single ophthalmologic examination within 4 weeks prior to completion of study participation (Section 9.1.7), except for those subjects who have withdrawn consent or assent (Table 3-2). This examination should be completed within 4 weeks before the Week 52 Visit, unless the subject prematurely discontinues study drug, in which case this examination should occur by the Safety Follow-up Visit (or ETT Visit for subjects who do not complete a Safety Follow-up Visit), as described in Section 9.1.5.

Any clinically significant abnormal findings will be reported as AEs.

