8.4 Safety Analysis

All safety analyses will be based on data from the TE Period for the Treatment Period for all subjects in the Safety Set for the Treatment Period, unless otherwise specified. Subjects will be analyzed according to the treatment they actually received in the Treatment Period, as applicable. Subjects receiving study drug from more than one treatment group will be allocated to the VNZ/TEZ/D-IVA group.

The overall safety profile of the study drug will be assessed in terms of the following safety and tolerability endpoints:

- Treatment-emergent adverse events (TEAEs)
- Clinical laboratory values
- ECGs
- Vital signs
- Pulse oximetry
- Ophthalmological examinations (for subjects <18 years of age on the date of informed consent)

Only descriptive analysis of safety will be performed, and no statistical testing will be performed.

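### Cataract is an adverse event of special interest, but no planned table gives its incidence in the under-18s, the only subjects with scheduled eye examinations

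*SAP*

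**What the plan says.** Protocol 12.3.4 lists cataract among the special-interest events: "LFT elevations, creatine kinase elevations, rash, cataracts, hypoglycemia, and neuropsychiatric events will be designated as AEs of special interest". SAP 8.4.8.1 repeats this, and SAP Appendix G gives the preferred terms, which include lens discolouration and lenticular opacities.

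Protocol 11.6.6 limits who is examined: "Ophthalmologic examinations will be conducted only for subjects who are <18 years of age on the date of informed consent". After screening there is one further examination for subjects under 18, and the rule reads: "completed at least 12 weeks of study drug treatment will have a single ophthalmologic examination within 4 weeks prior to completion of study participation". Anyone who withdraws consent or assent is exempt. The same section adds: "Any clinically significant abnormal findings will be reported as AEs".

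For the analysis, SAP 8.4 sets the default: "All safety analyses will be based on data from the TE Period for the Treatment Period for all subjects in the Safety Set". The set meant is the Treatment Period one, which SAP 7.4 defines as everyone dosed at least once in that period, whatever their age. SAP 8.1 has categorical variables shown as counts and percentages. SAP 8.4.8.1 then says "For AESI during the TE Period for the Treatment Period, the following categories will be summarized by treatment group" and states no other analysis set. The examinations themselves are not tabulated: "Ophthalmologic examination results will be presented in individual subject data listings only" (SAP 8.4.6).

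**The concern.** Lens changes are actively looked for in one part of the trial population and only passively reported in the rest. Subjects under 18 have a dilated slit-lamp examination at screening and, if eligible, once more near the end of participation. Subjects aged 18 or over have no scheduled eye examination by an ophthalmologist or optometrist. For them, cataract enters the data only if it comes up in routine adverse event questioning or other care. The default denominator puts both groups together, so adults whose lenses were not examined count as subjects without cataract.

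What is at stake is the absolute incidence and the absolute difference between arms for a designated risk. Both shrink as the adult share grows. A table with no cases is also easily read as evidence from about 200 subjects per arm, when lenses were examined in far fewer.

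**Working it through.** The documents give no cataract incidence, no expected share of subjects under 18 and no cataract-specific denominator, so there is no figure of the plan to reproduce.

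**Inputs**
- About 400 subjects randomized 1:1, so about 200 per arm (SAP 6.3).
- f = share of an arm under 18. Age is a stratification factor, but no quota or expected share is given. Assumed range: 10% to 50%.
- pA = cataract incidence in subjects under 18; pB = incidence reported in adults. Both are assumed, for illustration.

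**Step 1: understatement of the percentage.** The all-ages percentage is f·pA + (1 − f)·pB. The understatement factor is pA / [f·pA + (1 − f)·pB], which reduces to 1/f when pB = 0.

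| f (n under 18 of 200) | pB = 0 | pA = 5%, pB = 0.5% | pA = 2%, pB = 0.5% |
|---|---|---|---|
| 10% (20) | 10.0 | 5.3 | 3.1 |
| 20% (40) | 5.0 | 3.6 | 2.5 |
| 30% (60) | 3.3 | 2.7 | 2.1 |
| 50% (100) | 2.0 | 1.8 | 1.6 |

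For example, with f = 20%, pA = 5% and pB = 0.5%: 0.2 × 5% + 0.8 × 0.5% = 1.4%, and 5 / 1.4 = 3.6.

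In counts, two cases, both in subjects under 18, would be shown as 2/200 = 1.0%. Among the under-18s they are 2/20 = 10.0%, 2/40 = 5.0%, 2/60 = 3.3% or 2/100 = 2.0%.

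**Step 2: no cases observed.** The exact two-sided 95% upper limit for 0/n is 1 − 0.025^(1/n).

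| n | Upper limit |
|---|---|
| 200 | 1.8% |
| 100 | 3.6% |
| 60 | 6.0% |
| 40 | 8.8% |
| 20 | 16.8% |

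**Step 3: comparison between arms.** With the same f and pB in both arms, the all-ages risk difference is f times the difference in the under-18s. The ratio is unchanged if pB = 0, and an adult background pulls it toward 1. With f = 20% and pA of 5% against 2%, the true difference is 3.0 points and the true ratio is 2.5. If pB = 0, the all-ages table shows 1.0% against 0.4%: a difference of 0.6 points and a ratio of 2.5. If pB = 0.5%, it shows 1.4% against 0.8%: again 0.6 points, with a ratio of 1.75.

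**The case against.** **Cataract is tabulated elsewhere.** A reader might infer that the AESI table is the only by-arm number for cataract, or that lens findings never reach a by-arm table. Neither is right. SAP 8.4.1 plans treatment-emergent event tables by system organ class and preferred term, where cataract terms will also appear by arm. Clinically significant examination findings must be reported as adverse events, and the Appendix G terms would capture those coded as lens opacities. Only findings judged not clinically significant stay in listings. However, the SAP 8.4.1 tables use the same all-ages default, so they do not supply the missing rate.

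**A signal need not be hidden.** Numerators are shown, so three cases against none remains three against none. Randomization is 1:1 and stratified at age 18, so both arms are diluted about equally. The listings allow the rate to be rebuilt by hand, and the data monitoring committee sees unblinded data by arm (SAP 9.2). This stands, and it limits the harm to absolute incidence and risk difference.

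**The denominator is inferred.** SAP 8.4.8.1 states neither percentages nor a denominator; both follow from the defaults in SAP 8.1 and 8.4. That is correct, but nothing in the SAP overrides those defaults for cataract.

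**The table measures reported events, not examination results.** An event table does not claim that adults were examined and found clear. Adults are asked about adverse events at every visit (Protocol 13.1.1.3), and complete physical examinations cover the eyes (Protocol 11.6.3). This is fair, and it is why the all-ages row should stay. But neither is a dilated lens examination, and the planned output does not tell the reader that ascertainment differs by age.

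**Conclusion.** The point holds as a gap in the planned safety summaries. Following the SAP as written, no table gives cataract incidence in the population with scheduled lens examinations, and the all-ages percentage understates it.

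The size is conditional. It is 1/f if adults report no cataracts, which is 10 to 2 for an assumed under-18 share of 10% to 50%. In the illustrations with 0.5% reported in adults it is 5.3 to 1.6. A reader might conclude that incidence is diluted several-fold as a matter of fact. The documents do not support that, because they give no under-18 share and adults can report cataract too.

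Nor do they support a claim that the comparison between arms is badly distorted. Stratification by age largely preserves the ratio, apart from the effect of any adult background. What shrinks is the absolute incidence and the risk difference, and an absence of cases looks better supported than it is.

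**What to change.** In SAP 8.4.8.1 and 8.4.6, add one by-arm descriptive summary for Safety Set subjects under 18 at consent, showing:

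- treatment-emergent cataract AESI, and lens findings new since the screening examination;
- all such subjects as the main denominator;
- the number with a post-baseline eye examination, and the percentage among them as a second figure.

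The second denominator needs a note. It depends on at least 12 weeks of treatment and on consent not having been withdrawn, so it conditions on events after randomization and could differ between arms. For that reason it should not be the main one.

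Keep the all-subject row, with a footnote that subjects aged 18 or over had no scheduled ophthalmologic examination. The row should not be labelled as spontaneous reports, because it also contains events found at the scheduled examinations and events elicited by questioning.

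The SAP already restricts other summaries by age: treatment satisfaction to under-18s (8.5.1) and BMI z-score to subjects aged 20 or younger (8.3.4.2). SAP section 3 allows amendment before database lock. The cost is one extra table from data already collected, with small denominators and less favourable percentages. Study conduct, hypotheses and alpha do not change.
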